In this sense, some studies are being conducted on the use of mobile technology to control hypertension, aiming at greater access to the patient, education and awareness of the disease, as well as the patient's engagement in their care [29,30,31,32,33]. In a previously developed study, it was seen that virtual distance or face-to-face teaching, through "e-learning", helps to reduce the effect of the white coat and the anxiety of hypertensive patients, with an improvement in adherence to treatment [34].

However, it is not yet known the best technological tools to help hypertensive patients to improve treatment adhering to healthy life habits and, and consequently avoid the complications of AH. In addition, this tool needs to be feasible to be used by patients or caregivers, regardless of social class, preserving their intimacy, privacy and still obtaining the desired health improvement results.

Based on these arguments, the hypothesis of the proposal is that the use of an application developed by artificial intelligence adapted to individual needs and customs can help improve therapeutic adherence and provide better BP control in patients with uncontrolled hypertension.

2. Primary objective

To evaluate the effectiveness of an artificial intelligence application developed for home monitoring compared to institutional standard follow-up in patients with uncontrolled hypertension in the following parameters:

- a) To obtain adequate control of blood pressure (< 140/90 mmHg) of the office and of the blood pressure ambulatory monitoring (< 135/85 mmHg at wakefulness)
- b) Improving adherence to drug treatment assessed by a validated questionnaire

- c) Reduce dietary sodium intake and 24-hour urinary sodium
- d) Increase the performance of physical activity evaluated by number of daily steps
- e) Reduction of body weight and abdominal circumference

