3.1. Study design

Randomized study with patients with uncontrolled hypertension followed at the Outpatient Clinic of the Hypertension Unit of the Heart Institute (InCor-HCFMUSP), for the use of an application for monitoring and engagement to antihypertensive treatment - compared to the standard follow-up of the institution in a 12-month follow-up.

The study involves the direct participation of an institutional multidisciplinary team with an international partnership and a national institution of advanced technology in artificial intelligence. The hospital's team includes physicians, nurses, nutritionists, psychologists, physical educators and biomedical, supported by the institution's own innovation team. The international team includes all members of the Inavya Ventures LTd.

Will be included 100 patients diagnosed with primary arterial hypertension under drug treatment, with at least 3 classes of antihypertensive drugs in an optimized dose, aged 20 to 65 years, and who present clinic BP ≥ 140 and/or 90 mmHg, and wakefulness BP in ambulatory BP monitoring $\geq 135/85$ mmHg. Patients or their caregivers should also be able to use mobile phones and apps.

Patients with stroke sequelae or those with significant cognitive dysfunction will be excluded.

Randomization will be done in the 1:1 form using electronic randomization system, without knowledge by the team involved in the study. There will be two groups in the project,

so that, patients will be randomized to intervention group (application use) or control group (standard follow-up of the institution).

In the intervention group (N= 50), patients will receive a cellular device (by donation consigned by a telephone company) for the exclusive use of the application within 12 months. In this mobile device will be installed, with the guidance of the multidisciplinary team, the AVATR application developed in partnership with the company Inavya Ventures Ltd., where they will be digitized with individualized code for each patient, personal data, including age, gender, behavioral patterns and lifestyle habits (walks, type of diet, quality of sleep, etc.), and daily medications used.

The data will be allocated in a dedicated cloud and protected by cutting edge encryption. All this part of data capture and storage is in accordance with the rules of the General Data Protection Law (GDPL) as well as the General Data Protection Regulation (GDPR), the uk regulation.

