Patients will have a 15 days adaptation period to the use of the application, where they will receive virtual guidance by the multidisciplinary team for the correct use. After this period, patients will perform an evaluation by the medical and nursing staff, where clinical data (clinic blood pressure, weight, height and abdominal circumference) will be collected and patients will answer questionnaires on quality of life, anxiety, sleep quality, food intake and therapeutic adherence. In this same consultation, patients will receive an automatic blood pressure measurement device (described in the methods) to make household blood pressure measurement according to nursing guidance. Blood samples will also be collected for biochemical profile (total cholesterol and fractions, triglycerides, fasting glycemia, potassium, serum creatinine) and 24-hour urine sample for urinary sodium dosage, these tests will be collected at the Research Center and the analysis will be performed by the institute's laboratory.

The application automatically receives input data from each patient, such as BP MEASUREMENTS by the device and also the steps walked recorded by own in a third-party application also installed on the mobile phone. This data is safely transferred to the cloud server and analyzed based on an algorithm developed with the help of healthcare professionals to generate a customized lifestyle modification program designed for each patient. The application has automatic messages for the time of medication, in addition to strengthening nutritional guidance, physical activity and emotional order through automatic motivating phrases and also by access to educational videos. Another important tool is speech recognition that allows the patient to send data by voice system when there is difficulty in typing communication.

The multiprofessional team will receive alerts by email or the application platform, according to pre-established limits of blood pressure or symptoms, allowing immediate contact of the team for the necessary guidance. The multidisciplinary team will contact patients in the digital intervention group every 4 weeks for guidance based on the insertions made by patients in the application during the period. The correct use of medication as well as the adoption of healthy life habits will be reinforced in this contact.

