The control group (N= 50) will perform the same initial evaluation and answer the same questionnaires as described above for the intervention group. In this evaluation will receive guidance regarding the adoption of life habits by the multidisciplinary team. The control group will receive reinforcement of guidance only in clinic face-to-face visits.

The visits of the study after the patient's inclusion will take place every 12 weeks (Visits 2, 3, 4 and 5), totaling 4 visits after the initial visit, with the final visit after 12 months. Patients will perform 24-hour ambulatory blood pressure monitoring (ABPM) at visits 2, 3 and 5. In visits 2 to 5, the patient will have the measurement of blood pressure from the office, weight and abdominal circumference, and data on symptoms and events that occurred (hospitalizations, emergency room visits, symptoms) will be collected. In the last visit (12-month), in addition to these measures, the questionnaires performed on the first visit and laboratory dosages will be repeated.

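### Daily steps, primary parameter (d), is to be compared with standard follow-up, but no step count or physical-activity measure is described for the control group

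*Protocol*

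**What the plan says.** The primary objective (Protocol, section 2) evaluates the application "compared to institutional standard follow-up in patients with uncontrolled hypertension in the following parameters". Five parameters follow, and (d) reads "Increase the performance of physical activity evaluated by number of daily steps". Section 4, Expected results, again lists more physical activity among the gains expected relative to the institution's present follow-up. So (d) is a between-arm objective, and its measure is named.

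Section 3.1 says how steps are obtained. Of the 50 people allocated to the application it states: "patients will receive a cellular device (by donation consigned by a telephone company) for the exclusive use of the application within 12 months". The application receives "the steps walked recorded by own in a third-party application also installed on the mobile phone". No other source of step data appears in the protocol.

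For the control group (N = 50), section 3.1 says that patients "will perform the same initial evaluation and answer the same questionnaires as described above for the intervention group". For follow-up it says: "In visits 2 to 5, the patient will have the measurement of blood pressure from the office, weight and abdominal circumference", together with symptoms and events, and with ambulatory monitoring at visits 2, 3 and 5. At 12 months, "the questionnaires performed on the first visit and laboratory dosages will be repeated".

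On the timing of the first evaluation in the intervention group, section 3.1 says: "Patients will have a 15 days adaptation period to the use of the application". The clinical evaluation comes after that period.

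**The concern.** The objective asks for a difference between two arms in a quantity that the procedures record in one arm only. Followed as written, the trial would end with a series of step counts from application users and nothing to set against it. A report that the application increased physical activity relative to standard follow-up would have no control data behind it.

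This is not a detail that can wait for the statistical analysis plan. Such a plan can add a variable to a list or choose a model, but it cannot create observations that the visit procedures do not collect.

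**Working it through.** The protocol gives no figure to reproduce here, and the point does not depend on power or variance. The check is to trace each primary parameter to a measurement in the control group.

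| Primary parameter (section 2) | Control-group measurement described (section 3.1) |
|---|---|
| (a) Blood pressure control | Yes: clinic pressure and ambulatory monitoring |
| (b) Drug adherence | Yes: adherence questionnaire |
| (c) Sodium intake and urinary sodium | Yes: food recall and 24-hour urine |
| (d) Daily steps | None |
| (e) Weight and abdominal circumference | Yes: both |

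Result: 4 of 5 parameters have a control-arm measurement and 1 of 5 does not. Step data are described for up to 50 of 50 intervention patients and 0 of 50 controls.

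**Could the shared initial evaluation supply it?** No. It consists of clinical measurements, blood and urine samples, and questionnaires on five topics: quality of life, anxiety, sleep, food intake and adherence. None of these measures activity. The 12-month visit repeats the same questionnaires and laboratory tests, so it adds none either.

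**Do the instrument and analysis sections supply it?** No. None of the 10 measurement sections (3.2 to 3.11) describes a step counter or activity questionnaire. None of the 6 quantities named in section 3.12 (blood pressure, weight, body mass index, abdominal circumference, 24-hour urine sodium, questionnaire score) is a step count. Questionnaire score does not cover it, because no activity questionnaire is described.

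**Could the before/after comparison in section 3.12 replace the between-arm one?** No, for two reasons. It would not answer an objective set against standard follow-up. It also has no starting value: steps come from the phone supplied with the application, and no count before application use is described.

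**How late is the first evaluation?** Section 3.1 gives 15 days of application use beforehand. The timeline in section 5 puts training in months 2 to 3 and the data-collection consultation in months 5 to 6. Read per patient, the gap runs from 1 month (end of month 3 to start of month 5) to 5 months (start of month 2 to end of month 6). That timeline is drawn at study level, so the per-patient reading is an assumption. The finding does not depend on it.

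**The case against.** The strongest reply is that the protocol is silent on control steps rather than excluding them. Eligibility requires that patients or caregivers can use mobile phones and apps, so counts from controls' own phones might be obtainable. That is true, but being able to use a phone is not a collection procedure, and none is described. The conclusion is accordingly limited to the trial followed as written.

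Section 3.1 speaks of the application receiving data from each patient, and says that lifestyle habits, including walks, are entered in it. Both statements concern the application, which controls do not have.

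The counts from sections 3.2 to 3.11 and from section 3.12 are weak evidence on their own, and this part of the objection stands. Urinary sodium has no section of its own either, yet it is collected in both arms, and an analysis plan can complete a variable list. The evidence that carries the point is the account of procedures by arm in section 3.1.

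It is also fair to say that the stated hypothesis names therapeutic adherence and blood pressure control, not activity, and that those comparisons have data in both arms. This limits the seriousness of the gap but does not remove it. Finally, the documents do not say whether the objective or the procedure reflects the intention. Either could be changed, and the choice is the sponsor's.

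**Conclusion.** The concern holds. One of five primary parameters, (d), has no control-arm measurement (0 of 50 patients), so its between-arm effect cannot be estimated from the data the protocol describes. What can be reported is the course of steps among application users once they have started the application.

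This rests only on the procedures as written and on no outside figure. It does not mean that the other four parameters are free of difficulty: their first intervention-arm values come from the same visit after the adaptation period. They do have data in both arms. The point should be corrected, but it does not threaten the blood pressure comparison.

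**What to change.** Two wording edits bring the objectives into line with the procedures:

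1. Section 2: remove (d) from the primary between-arm comparisons, and state instead that steps recorded by application users in the intervention group will be described without comparison with controls.
2. Section 4: take increased physical activity out of the results expected relative to current follow-up, and draw no comparative conclusion on it.

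These edits need no new procedures. The price is one comparative primary objective (5 become 4).

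If the team prefers to keep the comparison, the same activity measure must be collected in both arms at matching times, first before application use starts and again at 12 months. It should be added to section 3 and to the variable list in section 3.12.

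- **Step counter or activity questionnaire in both arms:** 100 patients × 2 times = 200 added measurements, before dropout. With a counter and an assumed 7-day window this is 200 × 7 = 1,400 patient-days plus devices; the total scales directly with the window chosen. Wearing a counter may itself prompt some walking in controls. A questionnaire is cheaper, but patients who know their arm report their own activity, and (d) must be reworded because steps are no longer measured.
- **The same phone step recorder in both arms:** later intervention counts already reach the application, so the additions fall to 50 intervention values before use plus 50 × 2 = 100 control values, 150 in all.

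Whichever comparative option is chosen, the first measurement must come ahead of the adaptation period. For patients already using the application, that missing value cannot be recovered.

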3.12. Statistical analysis

All analyses will be performed based on the complete population of the set of analyses, and all values of the clinic BP and the mean wakefulness of the ABPM will be included. The

characteristics of the patient at the initial visit will be described using mean \pm standard deviation or median deviation (quartiles) for continuous variables, or number (proportion in %) for categorical variables. To compare the main variables before and after using the application, the appropriate tests will be performed according to the type of the variable, that is, whether quantitative or qualitative. Thus, to compare the quantitative variables (blood pressure value, weight, body mass index, abdominal circumference, 24-hour urine sodium and questionnaire score), a comparative analysis of a paired t-test will be performed. For the nonparametric variables, the chi-square and kruskall wallis test will be used to compare them.

4. Expected results

The use of the artificial intelligence application for distance monitoring of patients with uncontrolled hypertension should provide greater engagement of patients and their families in treatment, and thus may lead to better blood pressure control, greater adhering to healthy lifestyle habits (decreased sodium intake, increased physical activity and improved quality of life) when compared to the follow-up currently performed at the institution. Better blood pressure control of these patients, who generally require a high number of medications, may consequently reduce the risks of complications and also the search for emergency services, which can harm the patient, and also encumber the health service. In addition, the integrated participation of a multidisciplinary team more actively ensures greater involvement with patient care, without the need for frequent returns to the Unit for better blood pressure control.

5. Timeline

Month	Activity
1st to 2nd month	Selection of participants
2nd to 3rd month	Signature of the GDPL and training of patients with application
5th to 6th month	Consultation for data collection and delivery of the blood pressure measurement device
7th to 12th month	Monitoring patients by staff through the application
7th to 12th month	Consultation for data collection and delivery of the blood pressure measurement device

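### No step count is described from before application use, or for the control arm at any time, so the increase in daily steps in primary objective (d) has no clean reference value

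*Protocol*

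**What the plan says.** Section 2 of the protocol lists as primary objective (d): "Increase the performance of physical activity evaluated by number of daily steps". The stem that governs all the primary objectives makes this a contrast, with the application "compared to institutional standard follow-up in patients with uncontrolled hypertension".

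Section 3.1 gives one source of step data. The study application takes in "the steps walked recorded by own in a third-party application also installed on the mobile phone". On the phone itself, section 3.1 states for the intervention group: "patients will receive a cellular device (by donation consigned by a telephone company) for the exclusive use of the application within 12 months". The study application is installed on that device. Set-up entries include "lifestyle habits (walks, type of diet, quality of sleep, etc", which is a description of habits.

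The order of events is also in section 3.1: "Patients will have a 15 days adaptation period to the use of the application", and the initial evaluation comes after it. That evaluation covers clinic blood pressure, weight, height, abdominal circumference, questionnaires (quality of life, anxiety, sleep, food intake, adherence), blood tests and 24-hour urine. The control group has the same initial evaluation. Neither this list nor the list for visits 2 to 5 contains steps.

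Section 3.12 sets out the purpose of the analysis: "To compare the main variables before and after using the application". It assigns a paired t-test to a named list of quantitative variables, and steps are not on that list.

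**The concern.** An increase needs a reference value. The protocol offers two possible references, the period before application use (section 3.12) and standard follow-up (section 2), and describes step data for neither.

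For the before/after contrast, the phone that counts steps arrives with the intervention. The earliest possible counts therefore come from days on which the patient is already receiving guidance and using an application built to encourage physical activity. If walking rises quickly, part of the rise sits in the reference value and the measured change is too small. If walking peaks early and then settles, the measured change can be zero or negative even though patients walk more than they did before the study.

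For the contrast with standard follow-up, no phone or other step measure is described for the control group.

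This cannot be left to an analysis plan. An analysis plan can choose windows and models, but it cannot supply counts that were never recorded. The data collection is fixed in section 3.1 and has to be changed before phones are issued.

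**Working it through.** The protocol states no effect size, standard deviation, alpha or power for steps, so there is no figure to reproduce. The check is one of timing and coverage.

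**Order of events in the intervention arm (section 3.1)**

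| Stage | Step count described? |
|---|---|
| Before randomisation | No |
| Phone issued with the study application installed | Recording becomes possible |
| 15-day adaptation period, application in use | Possible, but not defined as a baseline |
| Initial evaluation | Not listed |
| Visits 2 to 5 (every 12 weeks) | Not listed; counts reach the application through the phone |

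The protocol gives no start date for step recording. The start is inferred: the phone is the only source described, so counts cannot precede its issue.

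**Coverage**

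- Intervention arm, before application use: 0 of 50.
- Control arm, before the intervention period: 0 of 50.
- Control arm, at any time: 0 of 50.

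**What an early-use baseline would do**

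Let D be the true change from before use to the end of follow-up, and f the share of D already present in the early-use window. Then

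measured change = D − f × D = D × (1 − f).

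The document gives neither D nor f. For illustration only, assume D = 1000 steps/day:

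| f (assumed) | Measured change (steps/day) |
|---|---|
| 0 | 1000 |
| 0.25 | 1000 × 0.75 = 750 |
| 0.50 | 1000 × 0.50 = 500 |
| 1.00 | 1000 × 0 = 0 |
| 1.25 (early peak, then decline) | 1000 × (−0.25) = −250 |

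For any f above 0 a true gain is understated. Nothing in the protocol narrows the range of f, so the direction can be argued but the size cannot be stated.

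**The between-group contrast**

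A randomised comparison of follow-up steps would not strictly need a baseline, which would mainly add precision. It does need follow-up counts in both arms, and the control arm has none. A pre-application count in the intervention arm would repair the before/after contrast but leave this one open.

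**The case against.** Several points on the other side have weight.

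- *Objective (d) is a comparison with standard follow-up, so the larger gap is the missing control-arm count.* This stands. A baseline in the application arm alone gives a pre/post change that mixes the application's effect with time, season and concurrent care. The fix must not be presented as answering (d) as worded.
- *Section 3.12 does not name steps for the paired t-test.* This also stands. The before/after analysis of steps rests on the general reference to the main variables and on the word increase in (d). Power calculations for a paired test of steps would describe a test the protocol does not assign to them, with inputs it does not give, so none are relied on here. Leaving steps outside section 3.12 does not help, because (d) would then have no stated contrast at all.
- *The adaptation period could serve as an early reference.* It could, but it is application use, and the protocol does not define it as a baseline.
- *Walking is recorded at set-up.* That entry is a lifestyle habit and not a number of daily steps.
- *Other measures share the problem, because the whole initial evaluation follows 15 days of use.* For those measures the protocol at least schedules an initial value. For steps it schedules none.

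A reader might go further and infer that the trial can show nothing about steps even within the application arm. The documents do not support that. With partial absorption the change is attenuated but not lost. Complete loss, or an apparent decline, requires f of 1 or more, and no passage points to such a value.

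**Conclusion.** The concern holds in this form: the protocol describes no step count from before application use, and none for the control arm at any time. Any early-use value, including one from the adaptation period, may already contain part of the effect. It would then bias the within-arm change by an amount that cannot be derived from the document. Objective (d) as worded, an increase compared with standard follow-up, is not supported by the data collection described.

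The coverage statement (0 of 50 in each arm before use, 0 of 50 controls throughout) comes from the protocol. It rests on one inference, that step recording cannot begin before the phone is issued. The step figures in the illustration are assumptions that show the mechanism and are not an estimate of its size.

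This affects one of five primary objectives and is cheap to repair before phones are issued. It should be corrected, but it does not bear on the blood pressure objective.

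**What to change.** 1. In section 3.1, issue the study phone with only the third-party step counter running for 7 days, and activate the study application after that. Take the mean daily steps over those 7 days as the baseline and the mean over the last 7 days before visit 5 as the follow-up value. Report the result as an uncontrolled within-arm change.
2. Claim a comparison with standard follow-up only if control patients' steps are counted in the same way over the same windows, for example with the same step application on their own phones. Eligibility already requires that patients or caregivers can use phones and apps, although that does not guarantee that each control patient carries a suitable one.
3. If neither is done, restate (d) in section 2 as a descriptive step trend during application use. Drop the claims of an increase from before use and of superiority over standard follow-up, and align the physical-activity statement in section 4.

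Cost: the run-in needs protocol wording and about one week's delay before activation, on the same donated phone. Its weakness is that counting may itself alter walking, so the baseline is not wholly untouched. Control-arm counting adds set-up and data transfer for 50 patients. The third option costs only wording and a weaker claim.

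### No ABPM is scheduled at the initial evaluation, so the planned before/after test of awake blood pressure has no sound before value

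*Protocol*

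**What the plan says.** Under section 2 (Primary objective), item (a) is adequate control "of the office and of the blood pressure ambulatory monitoring (< 135/85 mmHg at wakefulness"), compared with institutional standard follow-up.

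Section 3.1 makes an ambulatory recording part of eligibility: patients need a raised clinic pressure "and wakefulness BP in ambulatory BP monitoring" of at least 135/85 mmHg. It gives no date or maximum age for that recording and does not call it the baseline.

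The initial evaluation comes after a 15-day adaptation period with the application. It is a consultation "where clinical data (clinic blood pressure, weight, height and abdominal circumference) will be collected", together with questionnaires, blood samples and a 24-hour urine sample. ABPM is not among the items. The control group "will perform the same initial evaluation and answer the same questionnaires as described above for the intervention group".

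On later visits, section 3.1 says: "The visits of the study after the patient's inclusion will take place every 12 weeks (Visits 2, 3, 4 and 5), totaling 4 visits after" (that is, counted from Visit 1). On ambulatory recordings it says: "Patients will perform 24-hour ambulatory blood pressure monitoring (ABPM) at visits 2, 3 and 5".

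Section 3.12 states that "all values of the clinic BP and the mean wakefulness of the ABPM will be included". It then compares the main variables before and after application use, and lists blood pressure among the quantitative variables to be compared by paired t-test.

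**The concern.** A paired t-test needs a before value for each patient. Clinic pressure has one, because it is measured at the initial evaluation. Awake ambulatory pressure, the other half of the same objective, does not. Two candidates remain, and each distorts the paired change in its own direction.

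- **The eligibility recording.** Every patient was chosen because this reading was high. A repeat will be lower on average even if nothing is done, so the paired change overstates the effect.
- **The Visit 2 recording.** By then the intervention arm has used the application for 12 weeks on top of the adaptation period. Any effect already present is counted in the before value, so the paired change understates the effect.

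The protocol does not say which is meant. The answer decides whether the before/after result is biased up or down.

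**Working it through.** **1. Schedule.** Visits fall every 12 weeks after the initial visit, so ABPM is at week 12 (Visit 2), week 24 (Visit 3) and week 48 (Visit 5, described as 12 months). There is none at week 0.

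**2. Eligibility recording as the before value.** The protocol gives no mean, SD or repeatability for awake pressure, so these are assumptions: mean awake systolic μ of 135, 140 or 145 mmHg in the patients screened, SD 13, test-retest correlation r of 0.6, 0.7 or 0.8. Selection is simplified to systolic ≥ 135.

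With a = (135 − μ)/SD, λ = φ(a)/(1 − Φ(a)) and k = 1 + aλ − λ²:

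- expected fall on repeat with no effect = (1 − r) × SD × λ
- SD of the paired difference = SD × √[(1 − r)²k + (1 − r²)]
- chance of a significant paired t-test (n = 50, two-sided 5%) from the non-central t with non-centrality fall/(SD of difference/√50); this is approximate, because selected differences are not exactly normal.

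Largest case, μ = 135 and r = 0.6: a = 0, λ = 0.798, k = 0.363. Fall = 0.4 × 13 × 0.798 = 4.15 mmHg. SD of difference = 13 × √(0.16 × 0.363 + 0.64) = 10.86. Non-centrality = 4.15/(10.86/7.07) = 2.70, which gives 75%.

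| μ | r | Fall, no effect (mmHg) | Below 135 on repeat | Paired test significant |
|---|---|---|---|---|
| 135 | 0.6 | 4.1 | 29.5% | 75.4% |
| 135 | 0.7 | 3.1 | 25.3% | 61.5% |
| 135 | 0.8 | 2.1 | 20.5% | 44.0% |
| 140 | 0.6 | 3.0 | 21.0% | 46.5% |
| 140 | 0.7 | 2.2 | 18.0% | 35.9% |
| 140 | 0.8 | 1.5 | 14.6% | 25.1% |
| 145 | 0.6 | 2.0 | 13.8% | 23.5% |
| 145 | 0.7 | 1.5 | 11.9% | 18.5% |
| 145 | 0.8 | 1.0 | 9.7% | 13.7% |

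A different set of assumptions (mean 130 to 140, SD 12 to 15, r 0.7 to 0.9) gives falls of 0.7 to 4.6 mmHg and significant tests in about 14% to 87% of trials.

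**3. Visit 2 as the before value.** If a share f of a true effect δ is present at week 12, the paired change shows δ(1 − f). For assumed effects of 5, 8 and 10 mmHg and f = 0.5, it shows 2.5, 4 and 5 mmHg. For f = 1 it shows 0.

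**4. A fresh baseline as covariate.** Take three readings with equal pairwise correlation 0.7 and select on one of them. In units of SD²:

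- Adjusting for the eligibility reading leaves residual variance 1 − 0.7² = 0.51, whatever the truncation.
- For a fresh reading in the selected patients, the variance is v = 0.49k + 0.51 and the covariance with follow-up is c = 0.49k + 0.21. The residual variance is v − c²/v.
- μ = 135 (k = 0.363): v = 0.688, c = 0.388, correlation 0.56, residual 0.469, which is 8% below 0.51.
- μ = 145 (k = 0.562): v = 0.785, c = 0.485, correlation 0.62, residual 0.485, which is 5% below 0.51.

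**The case against.** A pre-application ABPM does exist for every patient, through eligibility. The list of Visits 2, 3 and 5 covers only visits after inclusion, so the natural reading is eligibility recording first, then those three. Visit 2 is a strained choice for a value before application use. Naming the baseline is often left to a statistical analysis plan, which may exist. This is fair as far as it goes. But such a plan can only choose among recordings; it cannot create one, and the more natural candidate is the one exposed to regression to the mean.

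It can also be said that objective (a) needs no baseline. All patients enter above the threshold, and the proportions below 135/85 at Visit 5 can be compared between randomised arms. This stands. A reader might infer that the randomised comparison is biased too; it is not, because regression to the mean acts on both arms alike.

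Two further inferences do not hold up:

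- **Large loss of precision.** Without selection, a correlation of 0.70 would remove 49% of the variance. The truncated eligibility reading correlates only 0.51 to 0.59 with follow-up and removes 26% to 35%. That comparison misleads, because a new recording would be made in the same selected patients and would reach only 0.56 to 0.62.
- **A recording 3 to 5 months old.** The timeline in section 5 puts selection in months 1 to 2 and the device-delivery consultation in months 5 to 6. Those are calendar blocks for the project, not intervals for a patient. The timeline is also marked as still to be validated, and it ends at month 12, so it cannot hold a 12-month follow-up that starts in month 5. What can be said is that no maximum age is stated.

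Finally, a better baseline does not turn a within-arm change into a treatment effect. That also stands, and the fix needs a between-arm analysis as well.

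**Conclusion.** The point holds for the before/after comparison of awake ambulatory pressure, the type of analysis that section 3.12 describes for blood pressure. With the eligibility recording as the before value, a fall of about 1 to 4 mmHg is expected with no effect, and the paired test is significant in roughly 14% to 75% of trials instead of 5%. With Visit 2, whatever effect arose in the first 12 weeks is lost. The millimetre and percentage figures rest on assumed mean, SD and repeatability, and on selection by systolic pressure alone; they show a range, not an estimate for this clinic.

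The point does not reach the between-arm comparison of awake control at Visit 5. The gain from a fresh recording as covariate is small, about 5% to 8% lower residual variance at a correlation of 0.7. Ageing of the eligibility recording could widen that gain, but the documents give nothing from which to size it.

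**What to change.** Move the Visit 2 recording to a baseline ABPM in both arms, taken after eligibility is confirmed and before the application is handed over. That means before the 15-day adaptation period, and ideally before randomisation. Adding it to the initial evaluation as now placed would not serve, because the intervention arm has by then used the application for 15 days. Keep the recordings at Visits 3 and 5. Use the new recording as the baseline covariate in a between-arm comparison, and keep the eligibility recording for selection only.

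The number of scheduled recordings stays at three. The cost is the 12-week ambulatory value, which section 3.12 would otherwise include, and a baseline recording to be fitted in before the application is handed over.

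If the sponsor prefers to keep Visit 2, name the eligibility ABPM as the baseline covariate in a between-arm analysis, state its maximum age at randomisation, and state that Visit 2 is never the before value. This costs only wording. It settles which value is used but does not remove regression to the mean from any within-arm change, so such a change should not be read as an effect of the application.
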